8.2.1.2 Adverse events

Adverse events (AE) for this study include the co-morbidities of prematurity listed above or any untoward medical occurrence deemed significant by the Principal Investigator. An AE does not necessarily have to have a causal relationship with this treatment. An AE may also occur which may be related to the medical device that is being tested. The Investigator will be asked to determine the causal relationship of each AE to the investigational device. This includes any event that is the result of incomplete user manual information or of incorrect use of the medical device.

8.2.1.3 Pre-existing Co-morbidities of Prematurity

A pre-existing condition or symptom/co-morbidity of prematurity prior to dosing is one that is present at the start of the study and is reported as part of the patient's medical history. A pre-existing condition or symptom should be reported as an AE only if its frequency, intensity or character worsens during study treatment.

All co-morbidities/AEs that occur from randomization through the discharge or 40 weeks PMA must be appropriately documented in the patient's medical chart and on the CRFs. When known, investigators should report syndromes rather than list symptoms associated with the syndrome.

AEs occurring in Part I should be followed until:

- resolution/stable sequelae; or
- the Investigator determines that it is no longer clinically significant; or
- the study patient is discharged.

If no follow-up is provided, the Investigator must provide a written justification.

8.2.2 Grading of Adverse Events

The severity of each AE will be categorized using the following criteria:

- Grade 1 (Mild): usually transient; requires no special treatment
- Grade 2 (Moderate): usually ameliorated by simple therapeutic measures
- Grade 3 (Severe): may require systemic drug therapy or other medical treatment

8.2.3 Relationship to Study Medication/Study Device/Study Procedure

The Investigator must assess the relationship of each reported AE. The Investigator must assess the relationship of the AE to the study medication using the following scale:

- **Unrelated**: The AE is definitely not or unlikely to be associated with study medication/study device/study procedure and is judged due to causes other than the study medication/study device/study procedure.
- **Related**: The AE is possibly or probably related with study medication/study device/study procedure.

8.2.4 AE/Co-Morbidities of Prematurity Action Taken

Any action taken in response to AE/co-morbidities of prematurity will be recorded as follows:

- Study Medication
 - Dose not changed
 - Drug interrupted
 - Dosing stopped
- Study Device/Procedure
 - None
 - Remove/Replace Controller
 - Remove/Replace Circuit

8.2.5 AE/Co-Morbidities of Prematurity Outcomes

The following terms and definitions are used in assessing the final outcome of an AE/Co-Morbidities of Prematurity:

- **Recovered/Resolved** - The participant has fully recovered, or by medical or surgical treatment, the condition has returned to the level observed at the first trial-related activity after the participant signed the informed consent.
- **Recovering/Resolving** - The condition is improving, and the participant is expected to recover from the event.
- **Recovered/Resolved with sequelae** - The participant has recovered from the condition, but with lasting effect due to a disease, injury, treatment or procedure. If a sequelae meets an SAE criterion, the AE must be reported as an SAE.
- **Not recovered/Not resolved** - The condition of the participant has not improved, and the symptoms are unchanged, or the outcome is not known at the time of reporting.
- **Fatal** - This term is only applicable if the participant died from a condition related to the reported AE. An AE with fatal outcome must be reported as an SAE.

8.2.6 Serious Adverse Events (SAEs), Treatment Emergent Adverse Events (TEAE), and Suspected Unexpected Serious Adverse Reactions (SUSARs)

8.2.6.1 SAEs

The Investigator is required to determine if each AE is a Serious Adverse Event (SAE). A SAE is any AE occurring after randomization through discharge from NICU or 40 weeks PMA and results in any of the following outcomes:

- Death, or
- Is life-threatening, or
- Requires inpatient hospitalization or prolongation of existing hospitalization, or
- Results in a persistent or significant incapacity or substantial disruption of the ability to conduct normal life functions

The Investigator is required to determine the causal relationship of each SAE to the investigational device based on the outcomes listed above in the definition of a SAE.

Important medical events that may not result in death, be life-threatening, or require prolongation of hospitalization may be considered SAEs when, based upon appropriate medical judgment, they may jeopardize the patient and may require medical or surgical intervention to prevent one of the outcomes listed in this definition.

In the event of death, the cause of death should be recorded as the SAE (death is an outcome, not the AE itself).

8.2.6.2 TEAEs

Treatment-emergent adverse events (TEAEs) will be summarized up to 7 days after birth and are defined as one of the following occurring from the first dose of AeroFact for the active group or from the first bolus instillation of surfactant in the control group:

- AEs that emerge during treatment, having been absent at pretreatment (Baseline), or
- Reemerge during treatment, having been present at Baseline but stopped prior to treatment, or
- Worsen in severity during treatment relative to the pretreatment state, when the AE is continuous.

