Efficacy Analyses	
The primary analyses of the primary, secondary, and additional efficacy endpoints will be conducted on the ITT population. The PP population analyses of primary, secondary, and additional endpoints will be considered supportive.
 
For the efficacy endpoints the data will be summarized and compared according to the variable type:
 
 Continuous data summaries will include: 
 Descriptive summary of number of observations, mean, standard deviation, median, and minimum and maximum values. Analysis of Covariance (ANCOVA) or Mixed Model Repeated Measures (MMRM) adjusted for stratification factors for inferential statistics. Categorical data summaries will include: 
 Frequency counts and percentages Logit model or Generalized Estimating Equation (GEE) method adjusted for stratification factors and clustering of multiple births within a mother for inferential statistics Time-dependent data: Cox proportional hazards model will be used to analyze time dependent data and to depict the time to event data.
Safety Analyses	
Safety will be evaluated on the Safety Population.
 
The number and percent of infants experiencing TEAEs, serious adverse events, and TEAEs leading to study discontinuation will be summarized for each treatment group by Medical Dictionary for Regulatory Affairs (MedDRA) system organ class and/or preferred term. Additional summaries will include TEAE severity and relationship to study drug.

PK Sampling	Not applicable

Table 1 – Schedule of Assessments and Procedures – Part I and Part II

Part I								Part II
		Day 1	Day 2-4	Day 5 – Day 28	36 Weeks PMA	40 Wks PMA	Discharge	3, 6, 9, 12 Months Corrected Age
Informed Consent ¹	X							
Demographics		X						
Maternal/Infant Medical History		X						
Chest Radiograph or Lung Ultrasound		X						
Medication History		X						
Inclusion/Exclusion Criteria		X						
Randomization		X						
Clinical Blood Gas Assessments ²		X	X					
Weight, Recumbent Length, Head Circumference ³		X					X	X
Administer AeroFact or begin nCPAP/nIMV alone ⁴⁻⁵		X	X					
Oxygenation and Respiratory Parameters ⁶⁻⁷		X	X	X	X ⁸	X ⁸		
Nasal Congestion Assessment ⁹		X	X					
Dosing Tolerance ¹⁰		X	X					
AE/Co-Morbidities Monitoring		X	X	X	X		X	
Concomitant Medications		X	X	X	X		X	
Feeding Status/Pulmonary Questionnaire/Audiology/Ophthalmology Reports							X	
Room Air Challenge (RAC) ¹¹					X	X		

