- For AeroFact patients in Part I and Part II, the median time-to-failure using AeroFact criteria was consistently numerically greater than for historical control patients.
- For AeroFact patients in Part II, the median time-to-instilled surfactant was consistently numerically greater than for Part II historical control patients.
- No patients in the AeroFact group or in the historical control group required instilled surfactant after 72 hours of life.

- For patients receiving AeroFact treatment in Part II, the proportion of patients requiring rescue with instilled surfactant was lower than for the matched historical controls (25% vs 45%); this corresponded to a relative risk of 0.56, in favor of AeroFact treatment.

Study APC-AF-CLN-001 overall conclusions:

- Administration of AeroFact, up to 4 doses within 96 hours of life, was shown to be safe and well tolerated in patients ranging from 26 2/7 weeks to 30 4/7 weeks of gestational age and with weights between 640 to 1,664 grams.
- No AeroFact-treated patients in Part I or Part II of the study, or among the matched historical controls, received instilled surfactant beyond 72 hours of life.
- The need for rescue therapy by instilled bolus surfactant was lower in Part II of the study compared with matching historical controls; 5 AeroFact patients (25%) in Part II required rescue with surfactant bolus instillations vs. 27 patients (45%) who required instillations in the matching historical control group; this corresponded to a relative risk of 0.56, in favor of AeroFact treatment.

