5.1 Inclusion Criteria

Preterm infants are eligible for this study if they meet all of the following criteria:

1. Parental consent obtained prior to study procedures being performed (pre-natal consent is allowed)
2. 26 0/7 to 31 6/7 weeks of gestational age
3. Weight < 2000 grams
4. Weight appropriate for gestational age (AGA 3% to 97%)
5. Age ≤ twenty-four hours at the initiation of study treatment (active or nCPAP/nIMV alone)
6. Current RSS (MAP x FiO₂) 1.4 - 2.0 (nCPAP or nIMV)
7. Chest radiograph or lung ultrasound [13,14] consistent with a diagnosis of RDS

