12.9.3 Safety Population

The Safety population is defined as all randomized subjects. This population will be used for the analysis of safety parameters.

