12.14 Safety Analyses

12.14.1 Adverse Events

Adverse events will be coded using MedDRA. TEAEs will be summarized for subjects who received at least one dose of AeroFact for the active group or received bolus instillation for the control group. AEs and TEAEs will also be summarized for up to 7 days after birth.

TEAEs will be summarized by treatment group, System Organ Class, and preferred term. The following TEAE summaries will be provided:

- TEAEs by severity grade
- TEAEs by relationship to study treatment.

In addition, separate summaries of serious adverse events, and adverse events resulting in discontinuation of study treatment will be presented.

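### Active-versus-control TEAE tables are not a randomized comparison: controls count only after a bolus, and the denominator is unsettled

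*Combined protocol and SAP*

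**What the plan says.** - **Start of counting.** Section 8.2.6.2 defines a TEAE as an event "occurring from the first dose of AeroFact for the active group or from the first bolus instillation of surfactant in the control group". The summary window closes 7 days after birth in every arm.
- **Who is in the table.** Section 12.14.1 says TEAEs are "summarized for subjects who received at least one dose of AeroFact for the active group or received bolus instillation for the control group". Tables by severity grade and by relationship to treatment are specified for TEAEs.
- **Denominator elsewhere.** Section 12.9.3: "The Safety population is defined as all randomized subjects. This population will be used for the analysis of safety parameters". Section 12.12 assigns all safety analyses to that population. The synopsis, under Safety Analyses, says: "The number and percent of infants experiencing TEAEs, serious adverse events, and TEAEs leading to study discontinuation will be summarized for each treatment group", also on the Safety population.
- **Control treatment.** Inclusion criterion 5 in section 5.1 limits age to "twenty-four hours at the initiation of study treatment (active or nCPAP/nIMV alone". The plan therefore treats continued nCPAP/nIMV as a study treatment with its own start.
- **AE collection.** Section 8.2.1.3: "All co-morbidities/AEs that occur from randomization through the discharge or 40 weeks PMA must be appropriately documented".

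**The concern.** The control group's treatment is nCPAP or nIMV alone. A control managed successfully that way has no TEAE period at all. A control who fails is counted only after receiving a bolus, which is a component of the primary endpoint (section 12.2.1). Active infants count from a dose given within 24 h of birth, whether or not they later need a bolus. Randomization therefore protects neither membership of the control column nor its start time.

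Pneumothorax shows the effect. Section 2.1 links nCPAP alone to pneumothoraces, and section 8.2.1.1 lists pneumothorax requiring a chest tube as an AE of interest. On day 2 in a dosed infant it is a TEAE. The same new event on day 2 in a control who has had no bolus is not.

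Safety and tolerability is a stated objective, and the dose and strategy chosen here go into Phase 3. A severity table whose columns differ by construction can make AeroFact look more or less harmful than control when there is no difference.

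**Working it through.** **Inputs from the protocol**
- Section 12.3: 87 randomized per arm, 82 completing; escalation 40% in control and 20% on AeroFact. The 40% is stated for treatment escalation and is used here as a proxy for control bolus use.
- Section 2.2.3.2 (Phase 2a): "27 patients (45%) who required instillations in the matching historical control group". It also reports that no AeroFact-treated patient "or among the matched historical controls, received instilled surfactant beyond 72 hours of life".
- Sections 4.1 and 8.2.6.2: first AeroFact dose within 24 h of birth; window ends at day 7.

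**Assumptions (not in the protocol)**
- 10% 7-day AE risk in every arm, so no true difference, with events spread evenly over the 7 days.
- All active infants dosed, at 12 h (range 6 to 24 h).
- Control bolus at 36 h. The range is 24 to 72 h; only the 72 h limit has document support.
- Control bolus use 40% (range 30% to 50%).
- Risk in failing versus other infants either equal or 3:1.

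**The plan's own figure.** For 40% versus 20%, two-sided 0.05, 80% power, pooled variance: n = [1.960·√(2×0.30×0.70) + 0.842·√(0.40×0.60 + 0.20×0.80)]² / 0.20² = 81.2, so 82. Then 82/0.95 = 86.3, so 87, and 3 × 87 = 261. The sample size reproduces and is not in dispute.

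**Controls who can contribute a TEAE**
- 40%: 0.40 × 87 = 34.8, leaving about 52 who cannot.
- 45%: 0.45 × 87 = 39.2.
- 30% to 50%: 26.1 to 43.5.

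**Expected TEAE percentages with no true difference**
- Active, dose at 12 h: 10% × (7 − 0.5)/7 = 9.29% (9.64% at 6 h, 8.57% at 24 h).
- Control, equal risk: 10% × (7 − 1.5)/7 = 7.86% of bolus-treated; × 0.40 = 3.14% of 87.
- Control, 3:1 risk: base risk 10%/(0.4×3 + 0.6) = 5.56%, so failing infants 16.67%. Then 16.67% × 5.5/7 = 13.10% of bolus-treated; × 0.40 = 5.24% of 87.

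| Scenario | Control, bolus-treated | Active/control ratio | Control, of 87 | Active/control ratio |
|---|---|---|---|---|
| Equal risk | 7.86% | 1.18 | 3.14% | 2.95 |
| 3:1 risk | 13.10% | 0.71 | 5.24% | 1.77 |

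**Range over bolus use, bolus time and risk ratio**
- Bolus-treated, lowest: 10% × 4/7 = 5.71% (equal risk, 72 h).
- Bolus-treated, highest: at 30% use and 3:1, failing risk is 30%/(0.9 + 0.7) = 18.75%; × 6/7 = 16.07% (24 h).
- Of 87, lowest: 0.30 × 5.71% = 1.71%.
- Of 87, highest: at 50% use and 3:1, failing risk is 30%/(1.5 + 0.5) = 15%; × 6/7 × 0.50 = 6.43%.
- Ratios with active held at 9.29%: 0.58 to 1.62 on bolus-treated, 1.44 to 5.42 on 87.
- Letting active also vary from 8.57% to 9.64%: 8.57/16.07 = 0.53 to 9.64/5.71 = 1.69, and 8.57/6.43 = 1.33 to 9.64/1.71 = 5.6.

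**Check without timing.** Take a 30% AE risk in the 40% of infants who would need a bolus and 10% in the rest. Active is 0.4×30% + 0.6×10% = 18%. Control is 30% of bolus-treated (ratio 0.60) or 0.4×30% = 12% of all (ratio 1.50). The denominator alone reverses the direction.

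**The case against.** The strongest reply is that most of the remedy is already planned. Section 12.14.1 also summarizes AEs, not only TEAEs, to day 7. Section 12.15.1 gives AE incidence by treatment group, and SAEs run from randomization. For incidence and SAEs this stands. The gap that remains is the severity and relationship tables, which are specified only for TEAEs. The relationship table gains less from the fix, because section 8.2.3 scores relationship to study medication, device or procedure, and controls receive no AeroFact.

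A second reply is that the start points are a deliberate exposure-based choice, pairing AeroFact with bolus surfactant as the tolerance assessments do, and that no test is attached. Such a summary is legitimate within a treatment. It does not justify setting the columns side by side by randomized arm.

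Third, the specific wording of section 12.14.1 may be read as overriding the general sections, and section 12 leaves detail to a separate SAP. That SAP text is not in the material reviewed. It could settle the denominator, but it could not change the start point without contradicting section 8.2.6.2. The bolus-treated denominator still leaves selection on outcome.

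Fourth, the sizes depend on assumptions. That is right. With a bolus at 12 h and equal risk, the ratio on bolus-treated controls is 1.0, so the later start is likely on average rather than certain. Inclusion criterion 5 is an age limit, not a TEAE definition, so it is only supporting evidence.

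**Conclusion.** The concern holds and should be fixed. Two defects are in the text whatever numbers are assumed: control entry and start time depend on a component of the primary endpoint, and the denominator is stated in two incompatible ways. At the plan's 40% rate, about 35 of 87 controls can contribute. Under the stated assumptions and no true difference, the apparent active-to-control ratio runs from about 0.5 to 1.7 on bolus-treated controls and from about 1.3 to 5.6 on all 87. Those ranges illustrate direction and order of size; they do not predict results. The damage is confined to the active-versus-control columns of descriptive TEAE tables. Efficacy tests, the SAE summary, the all-AE tables and the low-versus-high dose comparison, which shares one start point, are unaffected.

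**What to change.** In sections 8.2.6.2 and 12.14.1, define the between-arm AE set as events that start or worsen from randomization through day 7. Use all randomized infants as the denominator in every arm, and use this set for the incidence, severity and relationship tables. Keep post-dose and post-bolus tables as descriptive within-treatment summaries, each with its own stated denominator. Align the synopsis and sections 12.9.3 and 12.12 with this. In the same edit, settle the discontinuation table, which the synopsis describes as TEAEs leading to study discontinuation and section 12.14.1 as AEs resulting in discontinuation of study treatment.

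The cost is wording only: AEs are already documented from randomization in every infant, so no new data are needed. The small downside is that a few pre-dose events in the active arms will be counted. The change should be made before the Part I database is locked and dose allocation is unblinded to the sponsor.

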8.2.6.3 SUSARs

A Suspected Unexpected Serious Adverse Reaction is an AE or suspected adverse reaction is considered "unexpected" if it is not listed in the investigator brochure or is not listed at the specificity or severity that has been observed; or, if an investigator brochure is not required or available, is not consistent with the risk information described in the general investigational plan or elsewhere in the current application, as amended.

8.2.7 Reporting for SAEs

Part I

Regardless of causality, an SAE must be followed clinically until resolution or stabilization.

All SAEs after randomization through discharge from the NICU or 40 weeks PMA must be reported to the Sponsor or the Sponsor's representative within 24 hours of the investigational site's knowledge of the occurrence. The investigational site will either telephone the report to the Sponsor or the Sponsor's representative or transmit by email a Serious Adverse Event Report (SAER) to the Sponsor or the Sponsor's representative. If the initial report is made via telephone, a completed SAER must be emailed within 24 hours of the site's knowledge of the event. Investigational sites will be provided with SAER forms.

The SAER should be emailed within 24 hours with as much information as available at the time. At a minimum the initial report should include: patient number, event, treatment group (active or control), investigator assessment of causality, and event proximity to study drug dosing should be reported, if known. Supplemental information may be transmitted using a follow-up report and should not delay the initial report.

Part II

Only SAE's resulting in death will be recorded. Information on death will be collected and reported to Sponsor within 1 week of site notification.

9 PHARMACOKINETIC ASSESSMENTS

Not applicable.

10 SCHEDULE OF ASSESSMENTS AND PROCEDURES

The assessments and procedures for Part I and Part II of this study are described in detail below and presented in the Schedule of Assessments and Procedures located behind the Synopsis.

10.1 Part I

10.1.1 Consenting

Potential study patient(s) will be recruited by the study staff from hospitalized preterm infants 26 0/7 to 31 6/7 weeks of gestational age and who are at risk for worsening RDS. Prior to performing any study procedures or assessments, the nature of the study and the potential risks associated with the trial will be explained to the infant's parent(s) or legally authorized representative. An opportunity to ask questions will be provided to the parent(s) or legally authorized representative. Once all questions and concerns have been addressed by the study staff, a written informed consent will be obtained. A signed copy of the informed consent will be provided to the parent(s) or legally authorized representatives of the infant. Prenatal consent is allowed.

10.1.2 Screening (Assessment for Eligibility)

Preterm infants will be assessed for eligibility on Day 1. The following items will be assessed:

- Chest radiograph or lung ultrasound
- Gestational age and demographics (including date of birth, gender, race, and ethnicity)
- Medical history for mother and infant (including current medications)
- Birth weight, Recumbent Length, and Head Circumference
- Apgar Scores
- Respiratory support parameters (FiO₂, SpO₂, PEEP/CPAP pressure and flow rate, Paw, and Respiratory Support Status) (initial stabilization in delivery room, first stabilization in NICU, and one hour post nCPAP start)
- Qualifying RSS based on FiO₂ and CPAP calculated from parameters above
- Inclusion and exclusion criteria

The following items will be obtained prior to dosing:

- If a blood gas has been obtained for clinical purposes only, record PO₂, PCO₂, pH, bicarbonate prior to randomization/dosing, and/or as verification for meeting intubation criteria or in relationship to an SAE.
- Assess and document nasal congestion just prior to AeroFact dosing
- Evaluate identified Co-Morbidities of Prematurity prior to AeroFact dosing

If the baby has been assessed as eligible to participate in study and informed consent has been obtained, the baby may be enrolled into the study.

